1.7 Drugs/Devices/Biologics

Not applicable

1.8 Specimen Collection

Not applicable

1.9 Data Collection

A. Primary Data Collection

▪ Location:

Aim 1: Design sessions will take place on a remote platform such as Zoom.

Aim 1a: Cognitive interview sessions will take place on a remote platform such as Zoom.

Aim 2: For the first cohort, initial blood pressure reading for adult participants will take place in the emergency department at RWJ University Hospital in New Brunswick. The PI is faculty in the department and will discuss with the Chair of Emergency Medicine to determine the best method for collecting this information.

For the school cohort, questionnaires will be completed in person at the school (youth) or remotely (adults) via Redcap.

Aim 3: A questionnaire will be completed remotely, via digital badge platform, email, or phone.

In-depth interview data will be collected over the phone/Zoom.

▪ **Process of Data Collection:**

Aim 1: At the start of each design session, participants will complete a brief questionnaire, then participants will discuss the acceptability, feasibility, obstacles and solutions for digital badge implementation. Because sessions will be complete remotely, questionnaires will be completed electronically by participants directly on RedCap.

Design sessions will be led by the PI and participants will be asked to comment in an open-ended style with prompts used to guide the discussion. Prompts will help explore how long the intervention is likely to last, clarity of instructions, and likely reactions of participants. Each participant will be assigned a random study ID that will be associated with their responses so that their responses are de-identified. Design sessions are expected to last about 1.5 hours and will be audio recorded. The audio recording will then be transcribed by the RA.

Aim 1a: The participant will complete a brief demographic survey and then complete the hypertension knowledge tool on RedCap and will provide overall reactions and feedback. Then they will provide feedback on each question one at a time on wording, understandability, clarity, and relevance of instructions, items, and responses. Sessions will be led by the PI and RA. Sessions will last approximately 30 minutes and will be audio recorded. The audio recording will be transcribed by the RA.

Aim 2: For the first cohort, BP data will be collected when the potential participant is in the ED by the recruiter- either the RA or PI and will be entered into the RedCap study database. It will then be collected at 1 week and 2 months post-intervention when the adult participant returns to RWJUH for follow-up BP readings which will be entered into RedCap. HTN knowledge, self-efficacy, and self-care data will be collected electronically via RedCap. Participants will be sent a link to the appropriate questionnaires to be completed at baseline, 1 week post intervention, and 2 months post intervention.

For the school cohort, data collection will be done through Redcap. Questionnaires will be completed in person at the school (youth) or remotely (adults).

Aim 3: All participants in the intervention group will be asked to complete a questionnaire at the end of each intervention module through the digital badge platform, which will allow them to complete the questionnaire in RedCap. Participants must complete the questionnaires to receive their digital badge incentive.

We will also conduct one-on-one phone/Zoom interviews with interested participants for more in-depth information on intervention acceptability, feasibility, and fidelity. Interviews will last approximately 30-45 minutes each, be available in English and Spanish, and be audio recorded. The audio recording will then be transcribed by the RA.

▪ **Timing and Frequency:**

Aim 1: Participation will be a one-time design session.

Aim 1a: Participation will be a one-time design session.

Aim 2: For the first cohort, BP will be collected at baseline in the ED and at 1 week and 2-month post-intervention follow-ups at RWJUH. HTN knowledge, self-care, and self-efficacy will be collected at the start of the intervention, and at 1 week and 2 months post-intervention.

For the school cohort, youth and adult participants will complete study assessments after consent is signed. Fidelity of the intervention will be collected on youth the following week, and

youth will complete a HTN knowledge assessment at the end of this session. At the end of each of the 6 intervention modules, participants will complete module feedback assessments. At the end of the 6-week intervention and then 1 month after the end of the 6-week intervention, all participants will complete study assessments.

Aim 3: Implementation outcomes will be collected at the end of each module (questionnaires) and the end of the intervention period (6 weeks post-baseline). Interviews will take place at the halfway point and end of the intervention.

▪ **Procedures for Audio/Visual Recording:**

Aim 1: The design sessions will be audio recorded. This acknowledgement will be included in the consent/assent/parental permission form for participants of this aim (Group 1).

Aim 1a: The design sessions will be audio recorded. This acknowledgement will be included in the consent/assent/parental permission form for participants of this aim.

Aim 2: Not applicable

Aim 3: For intervention participants in who agree to participate in the in-depth interviews, the interviews will be audio recorded. This acknowledgement will be included in the consent/assent/parental permission form.

▪ **Study Instruments:**

Aim 1: *Quantitative:* Participants will complete a brief questionnaire of demographic information, HTN history (for adults), HTN family history, Williams et al. (1998)'s hypertension knowledge tool, and the Self-Reported Health Literacy Questions Among Diverse English and Spanish-Speaking Populations (Sarkar et al. 2011).

Qualitative: Design sessions will explore the acceptability and feasibility of the prototyped digital badge and web-based implementation process, including potential obstacles and solutions.

Aim 1a: A brief demographic survey and Williams et al. (1998)'s hypertension knowledge tool

Aim 2: For the first cohort, the primary outcome of the study is change in BP (in mm Hg). For both cohorts, we will collect secondary outcomes of pre- and post-intervention change in HTN knowledge, self-efficacy, and self-care (for adults) Additionally, we will ask adult participants to complete the Self-Reported Health Literacy Questions Among Diverse English and Spanish-Speaking Populations (Sarkar et al. 2011).Assessments are attached in eIRB. Assessments must be completed in order for participants to receive their study incentives.

Aim 3:

Quantitative: Participant outcomes will be measured from two sources: participant questionnaire and information pulled by the study team from the digital badge platform.

1. Participant questionnaire will include the following measures:
 - a. 4-item Acceptability of Intervention Measure (AIM) scale¹ to measure intervention acceptability by participants
 - b. 4-item Feasibility of Intervention Measure (FIM) scale¹ to measure intervention feasibility by participants
 - c. Amount of time spent for hypertension education module completion
 - d. Feedback on the hypertension education module.

[figure not shown]
2. Data pulled from the digital badge platform will measure intervention fidelity. This information will include:
 - a. Measures of adherence to program protocol: 1) # of participants who completed the entire digital badge, 2) Number of days between each XP (as XPs are meant to be administered weekly), 3) # pieces of submitted evidence rejected by the program reviewer for each XP
 - b. Measures of dose of intervention delivered: 1) Number of XPs completed in the playlist, 2) Which XPs were completed by participants who did not complete the entire digital badge

- **Qualitative:** Phone/Zoom interview participants will describe obstacles and successes that they encountered with the digital badge. We will also ask participants about acceptability and feasibility of the digital badge, including asking them to explain reasoning behind their favorite and least favorite module and most and least informative module.
- **Ethnographic Studies, Interviews, Or Observation:**
Aim 1: Design sessions will explore the acceptability and feasibility of the prototyped digital badge and web-based implementation process, including potential obstacles and solutions.
Aim 1a: We will recruit a subset of interested youth from the design session participants (Aim 1) for the one-on-one youth cognitive interviews, which will take place over Zoom. The participant will complete a brief demographic survey and then complete the hypertension knowledge tool and will provide overall reactions and feedback. Then they will provide feedback on each question one at a time on wording, understandability, clarity, and relevance of instructions, items, and responses.
Aim 2: Not applicable.
Aim 3: Phone/Zoom interview participants will describe obstacles and successes that they encountered with the digital badge. We will also ask participants about acceptability and feasibility of the digital badge, including asking them to explain reasoning behind their favorite and least favorite modules and most and least informative modules.
- **Subject Identifiers:**
Aim 1: No identifiers will be collected. Questionnaires and audio recordings from design sessions will be de-identified and each participant will have a random study ID that will be used for both questionnaires and design session transcripts.
Aim 1a: No identifiers will be collected. Questionnaires and audio recordings will be de-identified and each participant will have a random study ID that will be used for both questionnaires and design session transcripts.
Aims 2 and 3: Data will be collected in REDCap (Research Electronic Data Capture)- a password protected, secure, web-based software platform designed to support data capture for research studies, providing 1) an intuitive interface for validated data capture; 2) audit trails for tracking data manipulation and export procedures; 3) automated export procedures for seamless data downloads to common statistical packages; and 4) procedures for data integration and interoperability with external sources. Redcap allows for removal of identifiers when research data is exported from Redcap for analysis, so we will remove identifiers prior to analysis.

B. Secondary Data Collection

Not applicable

1.10 Timetable/Schedule of Events (Aim 2- First cohort (ED recruitment))

(Please note that when RA approaches patient, they will ask patient if they know a 14-24 year old (not have a 15-18 year old living with them).)

2.0 Project Management

2.1 Research Staff and Qualifications

All members of the research team are faculty, staff, or students at Rutgers. The PI has years of experience planning and implementing research studies. Additionally, because this study is part of a career development grant, a highly qualified mentorship team of senior faculty members is in place to provide mentorship to the PI on all study aspects.

2.2 Research Staff Training

All research staff have completed requisite Collaborative Institutional Training Initiative requirements, and will obtain familiarity with the research protocol prior to any interactions with the study. This familiarity will be tested to determine readiness prior to interactions with the study and participants.

2.3 Resources Available

The study will recruit patients out of the emergency department (ED) at Robert Wood Johnson University Hospital (RWJUH). Uncontrolled hypertension is a prevalent condition in ED patients, and this ED sees 70,000 patients a year, so recruitment at this site can provide a large pool of eligible patients from which to recruit for this study. The PI is faculty in the department and has the support of the department chair to conduct this study in the RWJUH ED.

For the school cohort, we will recruit youth from NBHSTHS. The PI has worked with the school for one year for other projects and has the support and enthusiasm of the school's principal to conduct this study.

Additionally, this is a funded study and such funding supports hiring of a research assistant (RA), who will be a valuable asset to help the PI with such tasks as recruitment and data collection.

3.0 Multi-Center Research

Not applicable

4.0 Subject Considerations

4.1 Subject Selection and Enrollment Considerations

A. Method to Identify Potential Subjects

Aim 1: We will partner with the New Jersey Alliance for Clinical and Translational Science (NJ ACTS) community engagement core as a resource to help recruit participants for the user-centered design sessions from relevant community organizations. Community organizations will share the study and eligibility criteria with their constituents and will be asked to contact the PI for eligibility screening and scheduling into a design session. Youth will be recruited for design sessions from Rutgers youth summer programs, the CHAMPIONS program and Urban Health Program (which take place remotely from Chicago), and New Brunswick Health Sciences Technology High School. Leadership for the program/school will be given a flyer to distribute to students/program participants. Youth interested in participating in the study will contact the PI for eligibility screening (must be age 15-18 years), consent or assent + parental permission obtainment, and scheduling into a session. The recruitment flyer has been submitted as an attachment.

We will recruit adults with hypertension for the design sessions (Aim 1) from the Robert Wood Johnson University Hospital Emergency Department. Recruitment flyers will be displayed in the ED and ED providers will be given recruitment flyers to distribute to any adult patient who presents to the ED with elevated BP. Also, members of the study team will approach ED patients to inform them about the study, assess eligibility, and collect contact information into the interest form on Redcap (already approved).

Additionally, the East Brunswick Public Library will post the adult recruitment flyer. Interested people will contact the PI- [name] if interested in participating in a focus group. After reaching out, we will confirm eligibility with the potential participant. If eligible, we will then schedule them into a focus group or one-on-one interview session.

Aim 1a: Participants for this aim will be a subset of Aim 1 participants. Aim 1 participants who are youth or Spanish-speaking will receive a recruitment email about participation in Aim 1a, and can participate if interested.

Aim 2: For the first cohort, a member of the study team (usually the research assistant (RA)) will determine initial eligibility by checking the patient's chart/ED board for their BP. The RA will ask patients with BP $\geq 130/80$ mmHg if they have a history of HTN. If yes, the RA will ask the patient: 1) If they know a 14-24-year-old, and 2) If the youth has access to internet or a data plan, as well as a smart phone or computer (to complete the digital badge intervention).

For the school cohort, all students at NBHSTHS are eligible to participate if an adult in their life also wants to participate in the study.

Aim 3: All participants randomized to the intervention arm in the first cohort of Aim 2 and all participants in the school cohort will complete the implementation questionnaires for Aim 3, and those who are interested will participate in in-depth interviews after completing appropriate written consent for this element of the study.

B. Recruitment Details

Aim 1: We will partner with the New Jersey Alliance for Clinical and Translational Science (NJ ACTS) community engagement core as a resource to help recruit participants for the user-centered design sessions from relevant community organizations. Youth will be recruited for design sessions from Rutgers youth summer programs, the CHAMPIONS program and Urban Health Program (which take place remotely from Chicago), and New Brunswick Health Sciences Technology High School. Leadership for the program/school will be given a flyer to distribute to students/program participants. Youth interested in participating in the study will contact the PI for eligibility screening (must be age 15-18 years), consent or assent + parental permission obtainment, and scheduling into a session. The recruitment flyer has been submitted as an attachment.

We will recruit adults with hypertension for the design sessions (Aim 1) from the Robert Wood Johnson University Hospital Emergency Department. Recruitment flyers will be displayed in the ED and ED providers will be given recruitment flyers to distribute to any adult patient who presents to the ED with elevated BP. Also, members of the study team will approach ED patients to inform them about the study, assess eligibility, and collect contact information into the interest form on Redcap (already approved).

Additionally, the East Brunswick Public Library will post the adult recruitment flyer. Interested people will contact the PI- [name] if interested in participating in a focus group. After reaching out, we will confirm eligibility with the potential participant. If eligible, we will then schedule them into a session.

Aim 1a: Participants for this aim will be a subset of Aim 1 participants. Aim 1 participants who are youth or Spanish-speaking will receive a recruitment email about participation in Aim 1a, and can contact the PI to participate if interested.

Aim 2: For the first cohort, if the patient is eligible and interested in participating in the study, the RA will give the patient a study packet to bring home to the potential youth participant and will collect the patient's contact information. The patient will be asked to share the information with the youth and contact the study team if both adult and youth are interested in participating. If we have the youth's contact information from the adult, we will contact the youth directly and tell them that we received their information from the adult (see youth recruitment script) and see if they are interested in participating.

If the team does not hear from the patient or youth after 3 days, they will contact the patient to follow-up about participation. The adult patient and youth must both agree to participate in the study for the dyad to participate.

For the school cohort, we will recruit students at NBHSTHS for information sessions (see youth recruitment flyer). We will hold information sessions at the school about the study. After info session, student decides if they want to participate and determines if an adult in their life also wants to participate. Student will give their adult a recruitment flyer and will then complete a Redcap form with their info and adult's info including best time to reach adult to complete consent form and parent info for parental permission (if adult is not parent) on Zoom (could also complete at school if needed).

Aim 3: For recruitment of in-depth interviews, participants from the intervention group of the RCT (Aim 2 first cohort) and all participants in the school cohort will receive an email from the PI that describes the opportunity to participate in this additional study and how to contact the PI if interested in participation.

C. Subject Screening

- **Inclusion Criteria**

Aim 1: Participants will be youth (15-18 years) and adults (18+ years old) with self-reported HTN diagnosis.

Aim 1a: Participants will be youth (15-18 years) and Spanish-speaking adults (18+ years old) with self-reported HTN diagnosis.

Aim 2: First cohort: Eligible adult participants will be 18+ year old ED patients with a history of HTN and two high BP ($\geq 130/80$ mmHg) readings during their ED visit who have an existing relationship with a 14-24-year-old. The eligible youth participants (14-24-year-old) must have access to the internet or data plan and a smart phone or computer.

School cohort: Youth Eligibility: Any interested student at New Brunswick Health Sciences Technology High School.

Adult Eligibility: Adult (18+) (preference for adult who has been diagnosed with hypertension) with an existing relationship with the youth where it would be feasible to complete an online module together 1 hour per week for 6 weeks. Fluency in English or Spanish (youth must be able to speak fluent language).

Aim 3: Everyone who randomized to the intervention group for the RCT (first cohort) and all participants in the school cohort will be asked to complete a brief questionnaire after completing each module.. Interested participants from the intervention arm(first cohort) and anyone from the school cohort will be recruited for the in-depth interviews.

▪ **Exclusion Criteria**

Aim 1: Age <15 years, inability to speak fluently in English or Spanish

Aim 1a: Age <15 years, inability to speak fluently in English or Spanish

Aims 2 and 3: First cohort: Age <14 years, inability to speak fluently in English or Spanish, no access to the internet or a data plan and a smart phone or computer.

School cohort: People who cannot take part in the study are people who are not able to speak fluently in English or Spanish (youth and adult must be able to speak the same language), and youth with no access to the internet or a data plan and a smart phone or computer.

Aim 3: Participants from the control arm in the first cohort will not be eligible for the in-depth interviews or questionnaires.

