2. We will hold information sessions at the school about the study.
3. After info session, student decides if they want to participate and determines if an adult in their life also wants to participate. Student will give their adult a recruitment flyer and will then complete a Redcap form with their info and adult's info including best time to reach adult to complete consent form and parent info for parental permission (if adult is not parent) on Zoom (could also complete at school if needed).
4. Student consent, adult consent, and parental permission forms will be obtained using e-consent in Redcap.
5. Students will be grouped into a training session at school. At the start of the session, students will complete study assessments including demographics and hypertension knowledge in Redcap. (Adults will also complete their pre-intervention assessments remotely this week via Redcap.)
6. The following week, the student group will have a second in-school session to evaluate their knowledge on to implement the intervention on their adult at home by implementing it on a "practice adult" (one of the research assistants) who will have a checklist where they check off that the student is able to complete the intervention correctly and teach them anything that they have questions about or do not do correctly. Youth completes a HTN knowledge assessment at the end of this session.
7. For the following 6 weeks, students will implement the digital hypertension education intervention with their adult at home- completing one module per week (each module will take about one hour). (Participants will complete feedback assessments at the end of each module.)
8. At the end of the 6 weeks, adult and youth participants will again complete the assessments that they completed before the 6-week intervention (with the exception of demographics).
9. Halfway through the 6-week intervention and at the end of the intervention, any participants (youth or adult) who is interested (not required) can complete interviews about feedback on the intervention (on Zoom or in person).

10. 4 weeks after the end of the 6-week intervention, adult and youth participants will complete the assessments a final time.

Aim 3 (Group 2):

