Questionnaire: At the conclusion of each hypertension education module in the intervention, all participants in the intervention group will be asked to complete a questionnaire on the intervention's acceptability and feasibility as part of the requirement for module completion. Participants must complete the questionnaires to receive their study incentive.

Interviews: We will also conduct one-on-one phone interviews with interested participants from the intervention group for more in-depth information on intervention acceptability, feasibility, and fidelity. These will take place halfway through the intervention and at the end of the intervention. Interviews will be available in English and Spanish, and be audio recorded.

B. Data Points

Aim 1 (Group 1): Participation will be a one-time design session that will take place prior to the start of the RCT.

Aim 1a: Participation will be a one-time cognitive interview session.

Aim 2 (Group 2): For the first cohort, BP will be collected at baseline in the ED and at 1 week and 2-month post-intervention follow-ups at RWJUH. Pre- and post-intervention change in HTN knowledge, adult BP self-care, adult self-efficacy to manage HTN and youth confidence in managing adult BP will be collected during the same timepoints.

For the school cohort, youth and adult participants will complete study assessments after consent is signed. Fidelity of the intervention will be collected on youth the following week, and youth will complete a HTN knowledge assessment at the end of this session. At the end of each of the 6 intervention modules, participants will complete module feedback assessments. At the end of the 6 week intervention and then 1 month after the end of the 6 week intervention, all participants will complete study assessments.

Aim 3 (Group 2): Implementation data points will be collected at the end of each module (surveys) and at the midpoint and end of the intervention period (6 weeks post-baseline) (interviews).

C. Study Duration

Aim 1 (Group 1): Participation will be a one-time design session that will last approximately 1.5 hours.

The duration of this aim is expected to be about 3 months.

Aim 1a: Participation will be a one-time cognitive interview session that will last approximately 30 minutes. The duration of this aim is expected to be about 3 months.

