4.3 Number of Subjects

A. Total Number of Subjects

Aim 1: Participants for the design sessions will be 10-15 adults in total and 10-15 youth in total. Each design session will be a focus group of approximately 5-8 people or one-on-one interview and we anticipate 2 design sessions for each group (adults and youth). One adult session will be in Spanish to be inclusive of participants with limited English proficiency.

Aim 1a: 15 participants

Aim 2: 100 participant dyads (1 youth + 1 adult = 1 dyad), 200 total

Aim 3: 10 adults and 10 youth will be recruited for phone interviews. In the first cohort, all members of the intervention group and in the school cohort all participants will complete questionnaires. () .

B. Total Number of Subjects If Multicenter Study

Not applicable

C. Feasibility

In the US, 33% of individuals have HTN⁶ and for adults with HTN, BP control decreased from 54% in 2013-2014 to 44% in 2017-2018.⁷ BP is elevated at almost half (44%) of all ED visits- compared to 27% of primary care doctor visits.⁸ Data demonstrates that ED patients' elevated BP is from HTN, and not a result of pain or anxiety from the ED visit.^{9,10} From 2006 to 2012, HTN-related ED visits made up 24% of all ED visits, and rose 5% per year.¹¹

Based on the high prevalence of uncontrolled HTN in the US, and especially in ED patients compared to patients in other settings, we anticipate that it will be feasible to recruit our study sample size of 100 patients for Aim 2 given we are recruiting from a large ED of 70,000 patients. (Aim 1 sample size of 20-30 participants is also feasible given the prevalence of HTN in the community.)

For the school cohort, there are about 200 students at the school, so we anticipate that recruiting enough students for the study will be feasible, especially because all study procedures will take place at school or at home.

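### The 10 adult and 10 youth interviews are filled by volunteers who answer an email, so people who stopped early may be few or absent, and no other source records why they stopped

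*Combined protocol and SAP*

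**What the plan says.** Each section that describes interview selection makes participation voluntary.

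- Section 4.1 A (Aim 3): "those who are interested will participate in in-depth interviews".
- Section 4.1 B (Aim 3): intervention-arm participants of the ED cohort and all school-cohort participants get an email telling them "how to contact the PI if interested in participation". The participant has to make the next move.
- Section 4.1 C (Aim 3): "Interested participants from the intervention arm(first cohort) and anyone from the school cohort will be recruited for the in-depth interviews".
- Section 1.3 A, school cohort: any participant "who is interested (not required) can complete interviews about feedback on the intervention".
- Section 4.3 A: "10 adults and 10 youth will be recruited for phone interviews".

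On timing, Section 1.3 A (Aim 3) says: "These will take place halfway through the intervention and at the end of the intervention". On purpose, Section 1.9 A says: "Phone/Zoom interview participants will describe obstacles and successes that they encountered with the digital badge".

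Two other Aim 3 sources are planned. A questionnaire on acceptability, feasibility, time spent and module feedback follows each completed module (Sections 1.3 A and 1.9 A). The badge platform supplies fidelity data, including "Which XPs were completed by participants who did not complete the entire digital badge". No section selects interviewees by completion status, reserves places, or provides a separate contact for people who stop.

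**The concern.** Non-completion is itself an Aim 3 outcome: Hypothesis 3 (Section 1.1 B) defines fidelity as a majority completing the whole playlist correctly. If a sizeable minority do not, the pilot will want to know why. The interviews are the place where obstacles are to be described, yet the places go to those who reply to an email. It is plausible, though the documents do not show it, that someone who has dropped the modules is less inclined to reply. If so, the interviews would mostly explain how the badge worked for those who stayed with it. The Framework Method named in Section 6.1 cannot recover accounts that were never collected, and reasons for stopping are hard to obtain once people have disengaged.

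**Working it through.** **Step 1: what each Aim 3 source can say about someone who stops.**

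| Source | Hears from a stopper? | Records the reason for stopping? |
|---|---|---|
| Module questionnaire | Yes, for each module finished; not for the module where they stopped | No |
| Platform data | Yes: modules (XPs) completed, days between them, rejected evidence | No |
| Midpoint interview | Possibly, if they volunteer | Only if they have already stopped by then |
| End interview | Only if they volunteer | Yes, if interviewed |

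So the reason for stopping reaches the study only through an interview, and an interview happens only if the stopper volunteers.

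**Step 2: how likely it is that none is interviewed.** The figure of 10 + 10 is set by the plan without a formula, so there is nothing to reproduce. The only documented input is 10 interviewees per group (Section 4.3 A). Two inputs are assumptions, because the documents give neither: the share *s* who stop early, and the willingness *r* of a stopper to volunteer relative to a finisher.

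Share of stoppers among volunteers: p = s·r / (s·r + 1 − s). Expected stoppers among 10: 10p. Chance of none: (1 − p)^10.

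| s | r | p | Expected of 10 | Chance of none |
|---|---|---|---|---|
| 0.30 | 1 | 0.300 | 3.0 | 0.7^10 = 0.028 |
| 0.30 | 1/3 | 0.10/0.80 = 0.125 | 1.25 | 0.263 |
| 0.30 | 1/10 | 0.03/0.73 = 0.041 | 0.41 | 0.657 |
| 0.20 | 1 | 0.200 | 2.0 | 0.8^10 = 0.107 |
| 0.20 | 1/3 | 0.0667/0.8667 = 0.077 | 0.77 | 0.449 |
| 0.20 | 1/10 | 0.02/0.82 = 0.024 | 0.24 | 0.781 |

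**Step 3: check with a finite pool.** Section 4.3 A plans 100 dyads but gives neither the split between cohorts nor the allocation ratio, so a pool of 50 to 100 people per group is assumed. Drawing 10 without replacement (hypergeometric for equal willingness, Wallenius noncentral hypergeometric otherwise) gives these chances of none:

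- equal willingness: 0.018 to 0.023 at 30% stopping, 0.083 to 0.095 at 20%, and 0.31 to 0.33 at 10%;
- one quarter as willing: 0.31 to 0.34 at 30% and 0.50 to 0.53 at 20%;
- one tenth as willing: 0.62 to 0.64 at 30% and 0.76 to 0.77 at 20%.

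The simpler formula is close enough for the purpose.

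**Step 4: both groups together.** If the adult and youth groups were independent, the chance of no stopper among all 20 would be the square of the figure for one group: 0.263² = 0.07 and 0.449² = 0.20 at one third; 0.657² = 0.43 and 0.781² = 0.61 at one tenth. Adult and youth work through the modules as a dyad and may well stop together. With such positive dependence the true value lies between the square and the single-group figure.

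**The case against.** The strongest reply is that the design is already open to stoppers. No criterion requires completion, the email goes to all intervention-arm and school-cohort participants, the $10 is paid per interview and not per module, and interviews are offered in English and Spanish. All of that is correct. A reader might infer that stoppers are excluded, or that the interviewees will all be finishers; the documents support neither.

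A reader might also infer that the interviews are the only Aim 3 source that hears from stoppers at all. That is wrong as well. Someone who stops after module 3 has already been asked for three sets of ratings and feedback. What is missed is the unfinished module and the reason for leaving.

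The midpoint wave is a further point against the concern, and the calculation does not model it. A participant interviewed at the midpoint who stops later has been heard on obstacles up to then, though not on the decision to stop.

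It is also fair to say that the size rests on two assumed inputs. If stoppers are as willing as finishers, the risk at 20% to 30% stopping is modest. Finally, no prespecified conclusion depends on the interviews: Hypothesis 3 is judged on scale averages and badge completion, and Section 1.5 declares a pilot. These points limit the severity. They leave the gap itself in place: no step secures an account from anyone who stopped.

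One more stronger reading is that the school cohort will take every place. Nothing apportions places between cohorts, so this could happen, but the documents do not show that it will, and it is a separate matter from early stopping.

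**Conclusion.** The point holds as a minor one. Selection by interest alone means that stoppers may be few or absent among the interviewees, and the reasons for stopping are recorded nowhere else. The chance of no stopper in a group of 10 runs from about 3% to 66% at 30% stopping, and from about 11% to 78% at 20% stopping, as relative willingness falls from equal to one tenth. Both the stopping share and the willingness ratio are assumptions, and the midpoint interviews are left out. Absence is therefore possible, and likely only if willingness is low or few people stop. The consequence is confined to how well Aim 3 can explain non-completion; the primary blood pressure comparison is unaffected.

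**What to change.** Keep 10 adults and 10 youth, and amend Sections 4.1 B, 4.1 C (Aim 3) and 4.3 A to state that:

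1. a lapse is defined in advance, for example from the days between modules that the platform already records, since the protocol has no such definition now;
2. participants whom the platform shows to have stopped before module 6 are invited to interview directly, at the time they stop;
3. a few places in each group are held for them (3 of 10 would be reasonable, but that is a judgment figure and not a derived one);
4. places still unfilled at a set date are released to other volunteers;
5. the report gives the numbers invited and interviewed by completion status and by cohort.

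The cost is protocol wording and a few extra contacts, with the same number of interviewees. Some places will fill more slowly. Invited stoppers may still decline, which is why item 4 is needed and why item 5 is worth having even if the reserved places go unused.
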